Cover Page

Protocol document version date Sept 27, 2021

Document submitted Nov 25, 2023

NCT # NCT06105138

Title: Cannabidiol Effects on Blood Alcohol Level and Intoxication

Statistical Analysis Plan

Prior to hypothesis testing, we will conduct data wrangling and visualizations on the raw data for all outcomes using the R programming language and packages included in tidyverse (Team 2013; Wickham et al. 2019) (e.g., ggplot2 (Wickham 2016)). To examine changes over time in BrAC, alcohol craving, affect, sedation, and stimulation during the descending limb of the BrAC curve (T2 – T8, see Figure 1) and to compare these changes by sex and condition, we will run a series of Multilevel Structural Equation Models (MSEM; (Mehta and Neale 2005) using Mplus 8 (Muthén and Muthén 2017). Due to the research design, where each participant completed each condition (placebo, 30mg CBD and 200mg CBD) and within each condition there were 7 repeated measures of interest, MSEM need to be run with a latent growth curve on the within-level to capture the change over time. Repeated measures of interest were taken at timepoints T2-T8, which represent the descending limb of the BrAC curve. We will focus on the descending limb because evidence suggests that some subjective effects of alcohol may be particularly prominent during the descending limb (Pihl et al. 2003; Brick 2006). In addition, prior medication studies have demonstrated that notable medication effects such as reduction in craving and stimulation are observed in both the descending and ascending limb (Ray and Hutchison 2007), but some unique effects such as increased tension may be specific to the descending limb (Ray et al. 2008). Another advantage of focusing on the descending limb is that changes during this time are expected to be approximately linear (e.g., BrAC decreases linearly (Posey and Mozayani 2007)), which supports a more straightforward interpretation of model results. Note that T2= 90 minutes after the start of the alcohol administration session and T8=4.5 hours after the start of the alcohol administration session.

In all models, condition will be treated as a within-person variable, and sex will be treated as a between-person variable. To examine whether condition influenced changes over time, we will regress the latent slope parameter defined by the latent growth curve model on a dummy coded within-person condition variable. As there are 3 conditions, each model must be run twice to assess all pairwise

comparisons. First with placebo as the referent group (i.e., comparing placebo to 30mg CBD and placebo to 200mg of CBD) and then again with 30mg CBD as the referent group (i.e., to get the comparison of 30mg CBD to 200mg CBD). To determine if sex moderates the condition → change relationship we will create a random slope of condition predicting the latent slope variable and then regressed that random slope on the between-person binary sex variable. This is referred to as the random coefficient prediction method (Preacher et al. 2010, 2016). We will also use this method to determine if the overall change over time is moderated by sex by regressing the random latent slope parameter on the between-person sex variable. The MSEM approach allows paths that include within-level effects to have random intercepts and allows for the creation of Bayesian credible intervals for assessing significance of effects. Bayesian credible intervals provide a robust test of direct and moderation effects, are computationally efficient, and are amenable to a variety of variable characteristics (e.g., hierarchical–nested and non-normal data; (Gelman et al. 2004; Muthén and Asparouhov 2012).

#1903 - Exploring the Effects of Acute Cannabidiol Administration on Blood Alcohol Level and Intoxication in Adult Human Subjects

Protocol Information

Review Type	Status	Approval Date	Continuing Review Date
Expedited	Superseded	Sep 27, 2021	--
Expiration Date	Initial Approval Date	Initial Review Type	
Aug 18, 2022	Mar 09, 2021	Full Board	

Feedback

Approval Comment

Amendment [v7] has been reviewed and granted approval by expedited review (§46.110(b)(2)) of minor changes on September 27, 2021. This amendment includes updated recruitment flyer CBD Alcohol Flyer 2. The IRB has determined that the risk level remains unchanged and the safeguards for participants is appropriate. The study was assessed as being in accordance with 45 CFR 46.111 of the 2018 Requirements.

RISK: More than Minimal

SPONSOR: CCTSI

Protocol Amendment Form

Amendment

Amendment Instructions

1. Complete this Amendment overview.

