Laboratory Sessions (CBD 30 mg Session, CBD 200 mg Session and Placebo-CBD Session). At each subject's first session, they will arrive at the lab at approximately 11:15am, undergo informed consent procedures with a trained research assistant, undergo urine pregnancy and drug screening and receive a breathalyzer test. We will use the Intoximeter Alcosensor IV Breathalyzer, which is the gold standard for alcohol research studies. Urine drug screening will test for the presence of illicit drugs (besides cannabis). If urine drug or pregnancy tests are positive, participants will be disqualified from participation. If BrAC is above 0.000, participants will be rescheduled. If all tests are negative, participants will complete a brief demographics form and psychological functioning/substance use questionnaires. Next, they do the first blood draw and will then be given either 30 or 200mg CBD dissolved in water or plain water (as the placebo CBD condition). They will then be asked to wait for 25 minutes in our lab. They will be provided with internet access during this time. Participants are allowed to consume water ad libitum throughout the entire day of the study. Immediately before the alcohol administration procedures begin, subjects will again have their blood drawn and will complete measures of balance/motor performance, inhibitory control, alcohol craving, stimulation and sedation. Specifically, the following measures will be administered to measure alcohol craving, stimulation and sedation: The Biphasic Alcohol Effects Scale (BAES) is a self-report rating scale measuring stimulant and sedative effects of alcohol. It has shown good reliability and validity in AUD. The Subjective High Assessment Scale (SHAS) is a standard self-report measure used to assess subjective responses to alcohol. The Alcohol Urge Questionnaire (AUQ) is a well-established measure of alcohol craving and desire to drink that is commonly used in the context of acute alcohol administration. To test balance/motor function we will use a psychomotor battery designed to capture measures of cognitive and motor impairment in divided attention, decision making, reaction time, motor tracking and balance movements following the intake of drugs or alcohol and designed to be administered repeatedly in a single session to assess changes in impairment without being susceptible to practice effects. Finally, to test inhibitory control we will use the The Flanker Inhibitory Control and Attention Task, which requires participants to focus on a stimulus while inhibiting attention to stimuli flanking it. These measures will be administered on an ipad. Next, participants will consume up to .8g/kg of vodka mixed with orange juice, following procedures from previous alcohol and cannabis co-administration studies. The dose will be reduced 8% for females to adjust for expected BrAC differences between males and females. An .8g/kg dose should produce a peak BrAC of no more than .089% approximately 1 hour after alcohol consumption, which should not significantly exceed the BrAC reached by heavy drinkers during a typical heavy drinking period. There will be a third blood draw at this time (approximately 1 hour after the start of the alcohol administration procedure). As in the three prior human studies of alcohol and CBD co-administration, participants will be asked to consume their alcohol within a 20-min. time period. The above procedures (breathalyzer measurement of BrAC, measures of inhibitory control and balance/motor performance, alcohol craving, stimulation and sedation) will be repeated every 30 min. for 4 hours post-alcohol administration. Participants will be required to reach a BrAC of <.03 before going home, which is estimated to take no more than 4 hours post-alcohol administration, given the elimination rate of alcohol from the body. They will also be required to either have someone pick them up from the lab after the study session is over, or if this is not possible our lab will call them a Lyft, and will cover the cost for them. Participants will be offered snacks after testing is complete to facilitate BrAC reduction. The visit will end at approx. 4:00pm. They will also be required to either have someone pick them up from the lab after the study session is over, or if this is not possible our lab will call them a Lyft. CBD Product. Consistent with the Colorado Department of Agriculture (CDA) and CSU regulations, the 30 mg and 200 mg CBD products will be sourced by Caliper Foods (<https://www.caliperfoods.life/>), which is a CDA compliant product containing <.3%THC (thus qualifying as hemp rather than cannabis, which means it is allowed on CSU's campus). Subjects will consume Caliper's 5% CBD concentrate liquid in water on the day of their CBD study appointment, and they will consume plain water with no CBD on the day of their placebo-CBD appointment. Caliper's CBD readily solubilizes into water within seconds and does not impact flavor, consistency, texture or appearance of the water. Thus, participants will not be able to tell whether they are consuming water containing CBD or plain water. Note that individuals who report very high levels of alcohol consumption on the questionnaires, those that report symptoms of severe depression or suicidality, or those that determine that they do need to seek alcohol treatment will be referred to the Psychological Services Center in the CSU Psychology Department (<https://psychology.colostate.edu/psc/>), Aspenridge recovery (<https://www.aspenridgefortcollins.com/>) and

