Risk of Phlebotomy. When having blood drawn, participants may experience some discomfort as a result of the needle prick in the arm. Some bruising or slight bleeding may occur. Although infection is possible, it is extremely rare, because the needle is sterile and disposable. Occasionally, people feel lightheaded or faint when blood is drawn, but the volume taken will be small (no more than 10mL is drawn for each of three blood draws). Protection Against Risks of Phlebotomy. Individuals trained in phlebotomy will conduct all blood draws. They have completed IBC training, BBP, BSL1, BSL2 and Hazardous Waste trainings and have demonstrated competence in phlebotomy, following the [name] lab's SOP. Individuals who may draw blood during the study are: [name], [name], [name], [name] and [name]. Risks of Alcohol Administration. Adverse effects of alcohol such as intoxication, acute mood shifts (e.g., feelings of sadness or depression), and odd perceptual experiences are possible. However, individuals are recruited because they are heavy drinkers, defined as consuming >5 drinks [>4 for women] per occasion) at least 5 days/month in the past 3 months. The dose of alcohol given in the study is only designed to bring BAC to a maximum of .089, which is not higher than a typical BAC reached by individuals drinking 4-5 drinks in a single occasion. Thus, individuals in the present study are not likely to experience alcohol intoxication beyond the level that they normally experience in their daily life as a heavy drinker. Protection Against Risks of Alcohol Administration. Several steps will be taken to minimize risk to participants as a result of the acute effects of alcohol including those based on guidelines provided by NIAAA (NIAAA Recommended Council Guidelines on Ethyl Alcohol Administration in Human Experimentation; NIAAA, 2005). More specifically, the following protections are in place: First, participants will be excluded from the study if they have a medical condition, have an alcohol use disorder (AUD) or another substance use disorder (SUD), are current in treatment for or seeking treatment for AUD or another SUD, or have a medical condition that may contraindicate the consumption of alcohol. Urinalysis drug screens will be used at both laboratory sessions to exclude for any illicit drug use. Participants will only be included in the study if they are current heavy drinkers who report 5 binge drinking episodes per month over the last three months (note that a binge is defined by SAMHSA as consuming 5 drinks per occasion [4 for women]). Study staff will closely monitor participant BAC via breathalyzer throughout the alcohol administration protocols to ensure that BAC never exceeds .089 (which is roughly the equivalent of four standard drinks and is at the legal limit for alcohol impairment) following established alcohol-administration procedures. Thus, the amount of alcohol provided over the sessions will not exceed the dosage level consistent with participants' normal drinking practices. At both laboratory visits, a picture ID will be required to prove age eligibility (> 21 years). Female participants will be required to take a private urine sample pregnancy test on the day of both laboratory sessions. In case of any positive reading, participants will not be eligible to participate. The results of all pregnancy tests will be kept confidential and the tests will be safely discarded. During the laboratory procedures, an experimenter will be present at all times. Participants will be required to remain in the laboratory until their BAC <.03 g/dL. Participants will be supervised by the experimenter during this period. Participants will also have an opportunity to ask questions of the experimenter. In addition, [name] (a trained clinical psychologist) will be on call during all study appointments if any participant experiences negative psychological effects. Risks of CBD Administration. There may be mild physical side effects of CBD consumption, including nausea, fatigue and irritability. In addition, CBD can increase the level in your blood of the blood thinner coumadin. Individuals will be screened out and not allowed to participate in this study if they are taking this medication.

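### The straight-line BrAC slope through T8 has no provision for readings of .000, so if sessions reach that floor, a CBD effect on BrAC level would be misread as a slower decline

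*Combined protocol and SAP*

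**What the plan says.** The Statistical Analysis Plan uses seven readings, T2 (90 minutes) to T8, where "T8=4.5 hours after the start of the alcohol administration session". It defends this window partly by shape: "changes during this time are expected to be approximately linear (e.g., BrAC decreases linearly". The CBD test is then on rate of change alone: "we will regress the latent slope parameter defined by the latent growth curve model on a dummy coded within-person condition variable". The SAP names no censored outcome, no rule for .000 readings and no condition effect on the latent intercept.

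Under Procedures, Laboratory Sessions, the protocol gives two figures that bear on how near the floor these readings come:

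- Peak: "An .8g/kg dose should produce a peak BrAC of no more than .089% approximately 1 hour after alcohol consumption". The dose is itself an upper limit: "Next, participants will consume up to .8g/kg of vodka mixed with orange juice". Risks and Benefits repeats the cap: "The dose of alcohol given in the study is only designed to bring BAC to a maximum of .089".
- Clearance: "Participants will be required to reach a BrAC of <.03 before going home, which is estimated to take no more than 4 hours post-alcohol administration".

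Both are limits. No elimination rate, mean peak or spread of peaks is given. Hypothesis 1 (Summary and Purpose) predicts lower BrAC under CBD over the whole 4-hour period and gives no size.

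**The concern.** A breathalyzer does not read below .000. BrAC can fall in a straight line only until it reaches zero, and it is flat from then on. A single slope fitted through T8 averages the falling part and the flat part. The earlier a session reaches zero, the flatter its fitted slope, so the slope comes to depend on the starting level.

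This matters because Hypothesis 1 concerns level. If CBD lowers BrAC by a constant amount and leaves elimination unchanged, CBD sessions reach the floor sooner than placebo sessions. The condition-to-slope path would then show a slower decline under CBD and could be reported as a change in alcohol elimination. A truly faster decline under CBD would be masked in the same way. The within-person design does not remove this, because the floor acts differently in the two conditions.

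**Working it through.** **1. Rate implied by the protocol's limits.** The 4-hour figure cannot be reproduced, since no elimination rate is stated. It can only be inverted. For a session at the peak limit that just meets .03 at 4 h:

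k = (.089 − .03) / (4 − 1) h = .059 / 3 = .0197/h.

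**2. Where that session stands at T8.** The result depends on how the SAP's session clock lines up with the protocol's, which the documents do not settle.

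| Clock | Peak to T8 | BrAC at T8 from .089 | Highest peak reading .000 by T8 |
|---|---|---|---|
| All times from start of drinking | 3.5 h | .089 − .0197 × 3.5 = .020 | .069 |
| Peak timed from end of the 20-minute drinking period | 3.17 h | .027 | .062 |
| T8 is 4 h after alcohol | 3.0 h | .030 | .059 |

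The session at the limit is therefore not at zero by T8. On the first clock it would need .089 / 3.5 = .0254/h to get there. Sessions peaking at or below about .06 to .07 would get there if they clear at .0197/h. At an assumed .015/h the first-clock threshold falls to .015 × 3.5 = .0525.

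**3. How level becomes slope.** Take k = .0197/h, the first clock, a placebo peak of .07 and a constant CBD reduction of .010. The least-squares slope is Σ(t − 3)y / Σ(t − 3)², with Σ(t − 3)² = 2(1.5² + 1² + 0.5²) = 7.

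- Placebo: BrAC at T8 is .07 − .0688 = .0012. Nothing is floored, and the slope is −.0197.
- CBD: BrAC at T8 would be .06 − .0688 = −.0088 but reads .000. This raises the slope by 1.5 × .0088 / 7 = .0019, to −.0178.

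The CBD slope is about 10% flatter although elimination is identical. With a peak of .06, the same reduction gives a slope about 19% flatter. With a peak of .08 or .089 it gives no difference.

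**4. False-slope rate.** This was simulated with a paired t-test on per-session slopes as a stand-in for the MSEM. All of the following are assumptions:

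- between-person peak SD .012, capped at .089; between-person rate SD .002/h
- session-to-session SDs of .005 (peak) and .0015/h (rate)
- reading error .002
- CBD reduction .010 with no true slope effect

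Both sample sizes are shown because Procedures gives 40 and Participant Population gives 20.

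| Rate per h | Mean peak | Peak to T8 | N=20 | N=40 |
|---|---|---|---|---|
| .015 | .08 | 3.5 h | about 6% | about 8% |
| .015 | .07 | 3.5 h | about 19% | about 31% |
| .0197 | .08 | 3.5 h | about 40% | about 70% |
| .0197 | .07 | 3.5 h | about 86% | about 99% |
| .0197 | .07 | 3.0 h | about 40% | about 63% |

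The share of sessions at .000 at T8 was computed with similar inputs but no session-to-session variation. It runs from 3% placebo and 11% CBD (.015/h, mean peak .08) to 73% and 90% (.0197/h, mean peak .06).

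With a reduction of .005, mean peak .07 and N=20, the false-slope rate is about 30% at .0197/h and 8% at .015/h. With no CBD effect it is 4% to 6%. Fitting only readings before the first .000 gives roughly 3% to 7% throughout.

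**The case against.** The strongest reply is that the documents do not put sessions at the floor. A reader might infer from the protocol's own figures that many sessions read .000 before T8. They do not show this: both figures are limits, and together they leave a session at the peak limit at .020 to .030 at T8.

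Applying .0197/h to a session peaking at .07 is a further assumption. Such a session needs only (.07 − .03) / 3 = .0133/h to meet .03 at 4 h, and it would then read .07 − .0133 × 3.5 = .023 at T8. At .0133/h and mean peak .07, about 7% of placebo sessions are at .000, and the false-slope rate is about 11% (N=20) and 13% (N=40). All of this stands, and it makes the point conditional.

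It is also correct that the artefact does not create a CBD effect from nothing. It arises only when CBD truly changes BrAC, and it then misstates a change in level as a change in rate.

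Two other defences carry less weight. The SAP plans to plot the raw data before testing, which would reveal a pile-up at .000 but commits to no action. It also describes Bayesian credible intervals as suitable for non-normal data, but an interval method does not correct a straight line fitted through flattened readings.

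Finally, handling the floor repairs the slope only. Hypothesis 1 is about level, and a condition contrast on level is a separate need.

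**Conclusion.** The point holds in conditional form. The SAP fits one straight line to BrAC through T8, tests CBD only on its slope, and has no provision for .000 readings. If sessions reach the floor and CBD lowers BrAC, the test confuses level with rate, always towards a flatter CBD slope.

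The size cannot be fixed from the documents. It rests on assumed peaks, clearance rates, spreads, clock and CBD reduction, and it runs from negligible (.015/h, mean peak .08) to a false slope finding in most trials (.0197/h, mean peak .07). That many sessions will be at .000 by T8 should not be stated as a fact about this trial. Because the harmful scenarios are plausible under an upper-limit dose and peak, and the remedy is cheap, the change should be made. Confidence is medium.

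**What to change.** In the SAP, for the BrAC outcome only:

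1. Prespecify a growth model that treats .000 as left-censored. A simpler alternative is to fit the slope to each session's T2 to T8 readings before its first .000. The two are not equivalent: censoring uses the information that a reading is at the floor, while truncation discards it. Name one as the analysis.
2. Report the number of .000 readings by condition and timepoint.
3. Qualify the linearity statement so that it applies only while BrAC is above zero.

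The cost is SAP wording and a model option or data-preparation step, with no new data, visits or participants. The downside is less precise slopes for sessions that reach zero early. If no session reaches zero, the result is unchanged.

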Cannabidiol, or CBD, is commonly found in the cannabis plant and has shown promise in treating alcohol use disorders (AUD). Several rodent studies show that CBD decreases alcohol intake. However, only three human studies have ever been conducted on this topic. These studies showed conflicting results regarding the impact of CBD on intoxication and blood-alcohol level. Importantly, existing studies have used synthetic CBD, which is dissimilar from the plant-based CBD products popular in the U.S. Thus, the conclusions that can be drawn from the existing work are limited, and tightly controlled human studies of the effects of plant-based CBD on blood alcohol level, psychomotor intoxication and subjective intoxication following acute alcohol consumption are needed. In this study, we will explore the effects of two doses of plant-based CBD (compared to placebo CBD) on blood alcohol level, motor and balance impairment as craving/desire for alcohol over the course 4 hours after subjects consume a standardized dose of alcohol. We hypothesize that in the CBD condition, blood alcohol level (estimated using a breathalyzer) will be lower, cognitive and motor/balance performance will be better and craving will be lower for all timepoints. These outcomes have implications for understanding the potential of CBD as an AUD treatment.

Describe the purpose for the proposed project.

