The purpose of the project is to improve our understanding of how plant-based CBD products may impact alcohol use among individuals who regularly use alcohol. Since alcohol and cannabis co-use is common in the U.S., CBD is commonly found in recreational and medical cannabis products, and animal research suggests that CBD may decrease alcohol intake, it is important to determine whether CBD have applications for reducing drinking in humans. Ultimately, this could have implications regarding the use of CBD as a potential treatment for alcohol use disorders. Primary objectives are to explore how CBD impacts blood alcohol level, as well as cognitive and motor performance during an acute alcohol administration session. Specific Aims are described in detail below: Aim 1. Assess effects of CBD+alcohol vs. placebo+alcohol on breath alcohol level (BrAC). Hypothesis 1. After consuming CBD, subjects will have lower BrAC throughout the 4-hour period compared to when they consume placebo CBD. Aim 2. Assess effects of CBD+alcohol vs. placebo+alcohol on subjective intoxication. Hypothesis 2a. After consuming CBD, subjects will experience decreased alcohol craving across all timepoints post-alcohol consumption compared to when they consume placebo CBD. Hypothesis 2b. Differences in self-reported stimulation and sedation effects will emerge in the CBD condition compared to the placebo condition across all post-alcohol consumption timepoints. We lack sufficient prior evidence to predict the direction of these effects. Aim 3. Assess effects of CBD+alcohol vs. placebo+alcohol on psychomotor intoxication. Hypothesis 3a. CBD will be associated with better performance on an inhibitory control task compared to placebo across all timepoints. Hypothesis 3b. CBD will also be associated with better balance/motor performance at all timepoints after alcohol consumption compared to placebo.

What do the investigators hope to learn from the project?

We hope to gain a better understanding of the impact of CBD on blood alcohol level. We also hope to better understand whether CBD impacts levels of acute alcohol intoxication (specifically as regards craving, subjective effects of alcohol and cognitive and motor impairment). This has implications regarding CBD's potential as a treatment for alcohol use disorder.

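### The SAP tests CBD only on the slope over T2–T8, but H1 and H2a predict lower levels of BrAC and craving, so neither hypothesis has a named test.

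*Combined protocol and SAP*

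**What the plan says.** The Statistical Analysis Plan section sets out to describe change over T2–T8 in BrAC, craving, affect, sedation and stimulation, and "to compare these changes by sex and condition". Its condition effect is a single path: "we will regress the latent slope parameter defined by the latent growth curve model on a dummy coded within-person condition variable". The model is run twice with different referents to obtain all pairwise comparisons. The sex-moderation step acts on that same condition-to-slope path. Intercepts appear only in a general remark that MSEM permits random intercepts. No regression of the intercept, mean level, area under the curve or individual timepoints on condition is stated.

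The protocol's Summary and Purpose section words the hypotheses differently:

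- **H1:** "subjects will have lower BrAC throughout the 4-hour period compared to when they consume placebo CBD".
- **H2a:** "subjects will experience decreased alcohol craving across all timepoints post-alcohol consumption compared to when they consume placebo CBD".
- **H2b:** differences in stimulation and sedation "will emerge in the CBD condition compared to the placebo condition across all post-alcohol consumption timepoints", with no direction given.

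The lay abstract in the same section repeats the level wording: "blood alcohol level (estimated using a breathalyzer) will be lower" and "craving will be lower for all timepoints".

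**The concern.** A slope contrast asks whether CBD changes how fast BrAC or craving falls. H1 and H2a ask whether BrAC or craving is lower after CBD. These are different parameters, and either can be zero while the other is not.

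If the plan is followed as written, two misleading outcomes are possible. H1 can be true while the only CBD test is null. Or a significantly steeper decline can be reported although BrAC was higher after CBD throughout the window. If the analyst then turns to the intercept, that choice is made without a stated rule and possibly after the results are known.

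H2b reads most naturally as a level claim too, but less explicitly, so the case rests on H1 and H2a.

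**Working it through.** The plan states no power, alpha or effect size for these contrasts, so there is no figure to reproduce. The finding rests on steps 1 and 2. Step 3 only illustrates its size.

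**1. Text.** In the SAP, condition predicts the latent slope and nothing else. H1 and H2a are about level.

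**2. Algebra.** The SAP gives seven measures, with T2 at 1.5 h and T8 at 4.5 h into the session. That is 3 h at 30-minute spacing. It expects roughly linear change. With t in hours from T2, write each condition as y = a + b·t. The gap (CBD minus placebo) is then Δa + Δb·t, and the slope test sees only Δb = (gap at T8 − gap at T2)/3.

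Assume a placebo line of 0.075 at T2 falling 0.018 per h, so T8 is 0.075 − 3 × 0.018 = 0.021 and the mean is 0.048. Four gap profiles:

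| CBD minus placebo | T2 | T8 | Mean | Slope difference per h | H1 within window |
|---|---|---|---|---|---|
| Lower, constant | −0.0080 | −0.0080 | −0.0080 | 0 | true |
| Lower, narrowing | −0.0125 | −0.0035 | −0.0080 | +0.0030 | true |
| Lower, widening | −0.0035 | −0.0125 | −0.0080 | −0.0030 | true |
| Higher, narrowing | +0.0125 | +0.0035 | +0.0080 | −0.0030 | false |

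Three profiles that satisfy H1 give a zero, a positive and a negative slope difference. The fourth contradicts H1 and gives the same slope difference as the third.

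**3. Illustrative rejection rates.** Sample sizes are N=40 (Study Overview) and N=20 (the anticipated total under Participant Population). The SDs are assumed: session level 0.010, session slope 0.003 per h, measurement 0.003. The test is two-sided 5% with a pooled residual on 2(N−1) df. This is a balanced-data stand-in for the Bayesian MSEM.

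- Level contrast: SE = √[2(0.010² + 0.003²/7)/N] = 0.00318 at N=20 and 0.00225 at N=40. The ratios 0.008/SE are 2.51 and 3.55.
- Slope contrast: Σ(t − 1.5)² = 2(0.25 + 1 + 2.25) = 7, so SE = √[2(0.003² + 0.003²/7)/N] = 0.00101 and 0.00072. For a difference of 0.0030 the ratios are 2.96 and 4.18.

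Simulation (10,000 trials per cell) agrees with these ratios:

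| Profile | Level test, N=20 / N=40 | Slope test, N=20 / N=40 |
|---|---|---|
| Lower, constant | about 69% / 94% | 5% / 5% |
| Lower, narrowing | about 69% / 94% | 81% / 98–99%, positive |
| Lower, widening | about 69% / 94% | 82% / 98–99%, negative |
| Higher, narrowing | not evidence for H1 | 82% / 98–99%, negative |

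Sensitivity to the assumed SDs:

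- Level SD 0.007 gives level power of 93% / over 99%. Level SD 0.015 gives about 37% / 65%.
- Slope SD 0.006 per h gives slope rejection of 32–33% / 58–59% for the non-constant profiles.

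The documents give no scale values for craving. On a scale-free basis, a constant reduction of 0.3, 0.5 or 0.7 SD of the paired difference has level power of 25%, 57% and 84% at N=20, and 46%, 87% and 99% at N=40. The slope test stays at 5% if no floor is reached.

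**4. Floor at zero.** The model above lets BrAC go below zero. Flooring it lowers the widening-gap slope rejection at N=20 from about 82% to about 74–76%. The constant-gap rate stays near 5–6%. A lower start changes more. Assume a T2 mean of 0.055 (between-person SD 0.012), visit-to-visit SD 0.006, decline of 0.015 per h (SD 0.002) and measurement SD 0.004, floored at zero. A constant reduction of 0.010 then gives a slope difference of +0.0011 per h and slope rejection of 29% / 54%. A true H1 effect would appear as slower decline under CBD.

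**5. A secondary, conditional point.** If the fitted model held intercepts equal across conditions, a constant drop of 0.008 would leak into the slope. In the step 3 variance model the expected bias is −0.0010, 0 or +0.0010 per h with time zero at T2, mid-window or T8. The SAP is silent on both the constraint and the time coding.

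**The case against.** The strongest reply is that the SAP is coherent on its own terms. It asks about changes and names the matching parameter, the Aims are broad enough to cover a rate effect, and the study is a pilot with no stated alpha or power resting on H1. The SAP also never says that a slope result will be reported as lower BrAC. All of this is true. But the protocol still states directional level hypotheses, and the SAP presents itself as a plan for hypothesis testing without revising them or linking any result to them.

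A growth model does estimate an intercept, so a level contrast is within reach. The SAP states neither a condition path to it nor where time is centred.

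The justification of the descending limb explains the window. It does not explain why only the slope is tested within it.

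Three points stand in part:

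- The rejection rates depend on assumed values and on BrAC staying above zero.
- The higher-but-narrowing profile shows what the slope cannot distinguish. Nothing in the documents suggests that it is likely.
- A mean-level test does not by itself establish lower values throughout. A gap running from −0.018 at T2 to +0.002 at T8 has mean −0.008 yet is not below zero at T8. The fix has to cover this.

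**Conclusion.** The concern holds and should be resolved before any conclusion is drawn on H1 or H2a. The plan names no test of either. That follows from the text and the linear model alone and needs no assumed value. Under the assumed SDs, with BrAC above zero, a constant reduction of 0.008 is found by a level test in about 69% of trials at N=20 and 94% at N=40, against about 5% for the slope test. A significant negative slope is equally likely, at 82% and 98–99%, under opposite truths about H1. These percentages move with the assumptions. The inability of the slope to settle H1 or H2a does not.

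There is also a limit of scope. T2–T8 covers 3 h and begins after the peak expected about 1 h after drinking, while H1 is worded for 4 h.

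**What to change.** In the same MSEM, also regress the latent intercept on the condition dummies, with time coded −1.5 to +1.5 h so that the intercept is the mean level over T2–T8. Then:

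- Name the 30 mg–placebo and 200 mg–placebo contrasts on this intercept as the tests of H1 and H2a and, without direction, of H2b. Keep the slope effect as a separate question about rate of decline.
- State that this tests average level over T2–T8, not every timepoint and not the full 4 h.
- If H1 and H2a are meant literally at every timepoint, also report the model-implied differences at T2 (intercept difference − 1.5 × slope difference) and at T8 (intercept difference + 1.5 × slope difference). Under linear change, both below zero means lower throughout the window.
- State a multiplicity approach for the two dose contrasts and across outcomes.
- Date the addition relative to unblinding, because the SAP describes the sessions in the past tense. If it comes after unblinding, label it so.

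Alternatively, if the question was deliberately changed to rate of change, restate H1 and H2 that way and draw no conclusion about lower BrAC or craving from the slope.

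The cost is SAP wording and one extra path per dummy, with no new data. It adds two contrasts per outcome, or 2 × 4 = 8 for BrAC, craving, stimulation and sedation. Unadjusted, two contrasts sharing one placebo carry about a 9% chance of at least one false positive. Testing each at 0.025 lowers level power in the illustration from 69% to 57% at N=20 and from 94% to 90% at N=40.
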